#### 3.5.3 Treatment Discontinuations

Subjects will receive study treatment until any of the reasons listed below are applicable. Subjects may discontinue study treatment at any time without prejudice. However, the subject will continue to be followed for safety as described in Section 5.3. For subjects who discontinue study treatment prior to disease progression per RECIST 1.1, disease assessments should continue per the protocol-defined schedule (Appendix A). For subjects who discontinue study treatment, every effort must be made to continue protocol-specified evaluations and follow-up (Appendix A) unless the subject also withdraws consent to participate in all aspects of the study (see Section 3.5.4). Otherwise, all subjects will be followed until a criterion for discontinuing radiographic tumor assessments is met (Section 5.5.6.1). Subjects will be followed for survival

status and receipt of subsequent anticancer therapy, radiation therapy or surgery affecting tumor lesion(s) after treatment discontinuation in order to capture all PFS events.

The following are reasons for discontinuation from study treatment:

- Subject no longer experiences clinical benefit as determined by the investigator (ie, radiographic PD, clinical deterioration attributable to PD and unlikely to reverse with continued study treatment and/or supportive care)
- Unacceptable side effects the investigator feels may be due to study treatment
- Specific AEs as described in Section 6.5.2
- The investigator feels it is not in the best interest of the subject to continue on study
- Participation in another clinical study using an investigational agent or investigational medical device
- Necessity for treatment with subsequent systemic anticancer therapy
- Receipt of local therapy for the purpose of retarding progression of the underlying disease
- Necessity for withholding study drug for greater than 6 weeks for AEs, unless continuation of treatment is approved by the Sponsor
- Refusal of sexually active fertile subjects (excluding subjects who have been sterilized) to use medically accepted methods of contraception
- Pregnancy of a female subject
- Request by the Sponsor
- Subject request to discontinue study treatment
- Unblinding of study treatment by the investigator (prior to the Maintenance Phase)
- Significant noncompliance with the protocol schedule in the opinion of the investigator or the Sponsor

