6.5 Study Treatment Exposure

Study treatment exposure will be summarized for all subjects in Safety population.

The following will be derived for each subject and descriptive summaries will be provided:

- Duration of exposure including dose holds in months, calculated as (date of decision to discontinue study treatment date of first dose of study treatment + 1) / 30.4375
- Average daily dose per subject (mg/day) of cabozantinib, calculated as (total dose received/duration of exposure)
- Percent dose intensity for cabozantinib calculated as 100*(average daily dose received mg/day)/(planned dose mg/day), where planned dose is either 140 mg/day or 60 mg/day.
- Duration of exposure excluding dose holds in months, calculated as [(date of decision to discontinue study treatment date of first dose of study treatment + 1)-(sum of all dose holds)] / 30.4375

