6.6 Study Treatment Modifications

Treatment modifications (holds and reductions) occurring due to AE will be summarized by treatment arm for subjects in the Safety population as follows:

A. Summaries for dose reductions due to AE

Categorical summaries for:

- Subjects with any dose reduction
- Cabozantinib dose levels (140 mg, 100 mg, 60 mg, 40 mg, 20 mg, 0mg) received by a subject, respective to treatment group
- Lowest cabozantinib dose level received (excluding dose holds)
- Last cabozantinib dose level received (excluding dose holds)
- Last cabozantinib dose level received (including dose holds)

Descriptive statistics for:

- Number of dose reductions
- Duration of treatment at each cabozantinib dose levels (140 mg, 100 mg, 60 mg, 40 mg, 20 mg, 0mg) received by a subject
- Time in days to first dose level reduction

- Time in days to second dose level reduction
- B. Summaries for dose holds due to AE:
 - Subjects with any dose hold, and dose hold ≥ 7 days, ≥ 14 days, and ≥ 21 days
 - Descriptive statistics for number of dose holds per subject, and classified into 1, 2, 3, and >3
 - Descriptive statistics for duration of dose holds per subject, calculated as (stop date of hold start date of hold + 1), and classified into ≥ 7 days, ≥ 14 days, and ≥ 21 days
 - Descriptive statistics for duration of total dose holds, calculated as (stop date of hold start date of hold + 1), and classified into \geq 7 days, \geq 14 days, and \geq 21 days
 - Descriptive statistics for time to first dose hold, time to first dose hold that was ≥ 7 days,
 ≥ 14 days, and ≥ 21 days. The time to dose hold is calculated as (start date of the hold first dose date + 1)
 - Descriptive statistics for time to second dose hold, time to second dose hold that was ≥ 7 days, ≥ 14 days, and ≥ 21 days
- C. Summaries for dose modifications (holds and reductions) due to AE:
 - Frequency counts and percentages for subjects with any dose modifications
 - Descriptive statistics for number of dose modifications per subject
 - Descriptive statistics for time in days to the first dose modification (see Appendix D)
 - Descriptive statistics for time in days to the second dose modification (see Appendix D)

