If year > year of the last dose: Set *month* and day to January 1st.

If year = year of the last dose: Set month and day to last dose date of study treatment + 1

If *year* and *month* are present and *day* is missing:

Set day to 1st day of month if the resulting imputed date is greater than date of last dose. Otherwise set the imputed date to date of last dose + 1

* Including concomitant and subsequent anti-cancer therapy, surgeries and procedures, and radiation, radionuclides & radiotracers.

Incomplete Study Treatment Start Date

Define previous sequential dosing "milestone" as the latest of previous dose stop date, previous dose hold stop date, date of first dose or randomization date. If *year* is missing (or completely missing): set to date of previous sequential dosing "milestone" + 1

If (year is present and month and day are missing) or (year and day are present and month is missing): set to January 1st

If year and month are present and day is missing: set to the first day of the month

If the imputed date is before the previous sequential dosing "milestone": set to the date of previous sequential dosing "milestone" + 1

Incomplete Study Treatment Stop Date

Define next sequential dosing "milestone" as the earliest of next dose start date, next dose hold start date, date of last dose from EOT CRF or the cutoff date.

If year is missing (or completely missing): set to date of next sequential dosing "milestone" - 1

If (year is present and month and day are missing) or (year and day are present and month is missing): set to December 31st

If year and month are present and day is missing: set to the last day of the month

If the imputed date is after the next sequential dosing "milestone": set to the date of next sequential dosing "milestone" -1

Incomplete Death Date

Identify date of last known alive (LA) prior to death from the following:

- 1. Date of decision to discontinue study treatment from End of Treatment CRF
- 2. Date of last radiographic assessment from End of Radiographic Follow Up CRF
- 3. Date last known alive from Survival Follow Up CRF
- 4. Date of last lab assessment from the Labs dataset

If year is missing (or completely missing): set to date of LA + 1

If only day is missing: set to the maximum of the first of month or LA + 1

If month and day are missing:

If year of LA = year of death

Set death date to date of LA + 1

If year of most-recent contact < year of death

Set month and day to Jan 1st

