Appendix D: Dose Modification Summary Definition and Algorithms

Define the following dose modification milestones:

A	Date dose first reduced due to AE	First date a dose was given that was > 0 and < assigned dose, due to AE
В	Date dose reduced again due to AE	First date a dose was given that was > 0 and < the level given at
		first reduction (A above), due to AE
С	Date dose first held due to AE	First date a dose record of 0 was entered, due to AE

Algorithms for selected summary items:

Template	Summary item	Algorithm
T_DOSERED	Time to first dose reduction due	Time from first dose to (A) above
	to AE	
T_DOSERED	Time to second dose reduction	Time from first dose to (B) above
	due to AE	
T_DOSEMOD	# of subjects with any	# of subjects with any of A or C (Counting unique
	modification due to AE	subjects: B is a subset of A)
T_DOSEMOD	# of unique dose level	Range of 0-3, counting incidence of A, B and C per
	modifications due to AE per	subject
	subject	
T_DOSEMOD	Time to first dose modification	Time from first dose to earliest of A or C (among those
	due to AE	with either A or C)
T_DOSEMOD	Time to second dose	Time from first dose to "second earliest" of A, B and C
	modification due to AE	(among those with 2 or more of A, B or C)

Notes:

- 1. For the purpose of counting the # of dose modifications and time to first and second dose modifications, only the first dose hold counts. But for dose hold summary all dose holds count.
- 2. The algorithm provided skips over dose increases and reductions back to a previously identified reduction. Also it is not possible for 2 dose holds to count as both a first and second dose modification.

Certificate Of Completion

Envelope Id: E2141CD162E744D2A06D9991B616F699

Subject: Please DocuSign: XL184-401-SAP-V2.docx

Source Envelope:

Document Pages: 49 Signatures: 5 Certificate Pages: 6 Initials: 0

AutoNav: Enabled

Envelopeld Stamping: Disabled

Time Zone: (UTC-08:00) Pacific Time (US & Canada)

Status: Completed

Envelope Originator:

PPD

PPD

IP Address: PPD

Timestamp

Sent: 03-Jun-2020 | 14:34

Viewed: 03-Jun-2020 | 18:27

Signed: 03-Jun-2020 | 18:27

Sent: 03-Jun-2020 | 14:34 Viewed: 03-Jun-2020 | 14:56 Signed: 03-Jun-2020 | 14:57

Record Tracking

Status: Original

03-Jun-2020 | 14:21

Holder: PPD Location: DocuSign

Signer Events

PPD

Exelixis, Inc. - Part 11

Security Level: Email, Account Authentication

(Required)

Signature

PPD

Signature Adoption: Pre-selected Style

Signature ID:

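### If the stop date of a final dose hold is incomplete, Appendix A's literal rule closes the hold before it began, so exposure excluding holds exceeds exposure including holds

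*SAP*

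**What the plan says.** - **SAP 6.5** gives two exposure durations, both running from first dose to the decision to discontinue. The second opens with "Duration of exposure excluding dose holds in months, calculated as [(date of decision to discontinue study treatment" and takes off all holds: "date of decision to discontinue study treatment date of first dose of study treatment + 1)-(sum of all dose holds". The minus sign between the two dates is lost in the text as read; I take it as subtraction here and in the next formula.
- **SAP 6.6 B** gives the length of a hold: "calculated as (stop date of hold start date of hold + 1". Holds are then classed as at least 7, 14 or 21 days.
- **SAP Appendix A, Incomplete Study Treatment Stop Date**, limits such a stop by a next dosing milestone. Four dates can serve, and the rule takes "earliest of next dose start date, next dose hold start date, date of last dose from EOT CRF or the cutoff date". When the year or the whole date is missing, the stop is the milestone minus one day. If only the day is missing, it is the month end; if the month is missing, 31 December. Any imputed date later than the milestone is pulled back to the milestone minus one day.
- **SAP Appendix D** treats a hold as a zero-dose record; its hold milestone is "First date a dose record of 0 was entered, due to AE". Protocol 6.3 likewise has the CRF capture periods without dosing as intervals, and SAP 6.6 A lists 0 mg as a dose level with its own duration.
- **Protocol 3.5.3** foresees holds that end in discontinuation: one listed reason is "Necessity for withholding study drug for greater than 6 weeks for AEs, unless continuation of treatment is approved by the Sponsor". It also has the end-of-treatment CRF record the decision date and the last dose date separately.

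**The concern.** The two sections use different end points. SAP 6.5 counts the days between last dose and decision as exposure and relies on the hold total to remove them. The stop-date rule in Appendix A leaves out the decision date and includes last dose, which comes before a final hold starts. It has an upper limit but no lower one, although the matching start-date rule does have a floor at the previous milestone. Nothing prevents a stop date earlier than the start date of the same record.

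The summaries at stake are exposure excluding holds, total and per-subject hold duration, time at the 0 mg level, the hold tables by minimum length, and the time-to-hold summaries restricted to holds of a minimum length. Frequency of dose modifications is a named additional endpoint, and the rationale for 60 mg includes fewer interruptions, so these tables should be right.

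**Working it through.** The documents state no figure for hold length or exposure, so there is none to reproduce. I apply the rules to dates.

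**Inputs.** F = first dose (day 1); L = last dose; the hold starts at L + 1; D = decision date; C = cutoff. A month is 30.4375 days (SAP 4). Assumed values: L = day 335, about the 11-month median time on treatment in Protocol 3.2 (11 x 30.4375 = 334.8); D - L = 7, 28 or 42 days, the last being the 6-week limit; C one to three years after D. There are no earlier holds.

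**1. Stop date recorded as D.**
- Hold = D - (L + 1) + 1 = D - L.
- Exposure excluding holds = (D - F + 1) - (D - L) = L - F + 1, first to last dose, as it should be.
- With a 42-day gap, D = 377: hold 42 days; exposure including holds 377 days (12.39 months); excluding holds 335 days (11.01 months).

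**2. Stop date incomplete, literal rule.**
- There is no later dose or hold, so the earliest listed date is L, and the stop is L - 1. A partial date gives the same result: its imputed month end or year end falls after L and is pulled back.
- Hold = (L - 1) - (L + 1) + 1 = -1 day.
- Exposure excluding holds = (D - F + 1) + 1, one day more than exposure including holds.
- Overstatement = (D - F + 2) - (L - F + 1) = (D - L) + 1 days.

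| D - L (days) | Including holds (days) | Excluding, correct (days) | Excluding, literal (days) | Overstatement |
|---|---|---|---|---|
| 7 | 342 | 335 | 343 | 8 days = 0.26 months |
| 28 | 363 | 335 | 364 | 29 days = 0.95 months |
| 42 | 377 | 335 | 378 | 43 days = 1.41 months |

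The overstatement does not depend on L; L = day 90 gives the same errors.

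**3. Stop date incomplete, last dose skipped because it is not a next date.** The only milestone left is C.
- Year or whole date missing: stop = C - 1. With the 42-day gap and C one year (365 days) after D, the stop is day 741, the hold is 741 - 336 + 1 = 406 days, and exposure excluding holds is 377 - 406 = -29 days (-0.95 months). At two and three years the holds are 771 and 1136 days and exposure is -394 and -759 days (-12.94 and -24.94 months).
- Only the day missing: the stop is the month end, so the error is under a month.
- Month missing: the stop is 31 December, so the error is under a year.

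**4. Hold followed by a restart.** The earliest milestone is the next dose start, and a fully missing stop becomes the day before it. This is correct.

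**The case against.** **The formula in SAP 6.5 is sound when dates are complete.** That stands. A reader might infer that every hold ending in discontinuation is mismeasured. Step 1 shows otherwise, and nothing in the documents says these stop dates are left open. Protocol 6.5.1 asks for modifications to be entered within 72 hours, and SAP 11 plans data validation and a review of anomalies before lock. A negative hold is something such checks could catch.

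**The rule may not cover holds.** Its heading does not name them, and Appendix A lists dose dates and hold dates as separate items. Against that, holds are zero-dose records and Appendix A has no other rule for closing them. If the rule does not apply, an open final hold has no rule at all, and the same amendment fills the gap.

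**A last dose before the hold is not a next milestone.** This is a fair reading, but it leads to step 3, which is also wrong. A reader might take the multi-year hold as the main result. It is an alternative to the literal reading, not an addition to it, and needs the year or whole date missing. SAP 4.4, which limits imputation to partial dates, also sits uneasily with imputing a fully missing stop, though Appendix A does so explicitly.

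**The effect on the comparison of arms is unknown.** A reader might infer that 140 mg would look better tolerated than it is, or apply the pooled 15.1% AE-discontinuation rate in Protocol 1.4.3.1 to get about 14 of 94 subjects per arm (0.151 x 94 = 14.2). The documents do not support either step. The rate is pooled over single-agent studies, not every such discontinuation follows a hold, and the share with incomplete stop dates is not given.

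**Conclusion.** The point holds as a conditional defect. When a final hold has an incomplete stop date and the Appendix A rule is applied to zero-dose records, following the text literally gives a hold of -1 day and exposure excluding holds that exceeds exposure including holds. The overstatement per affected subject is 0.26 to 1.41 months for gaps of 7 to 42 days. The other reading gives an error of under a month if only the day is missing, and can give negative exposure if the whole date is missing.

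This assumes that the hold starts the day after last dose and that an end-of-treatment last dose date is recorded. How many subjects would be affected cannot be derived from the documents.

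Only descriptive exposure and hold-duration summaries are touched. PFS, ORR, the count of holds and the unrestricted time to first hold do not use the imputed stop. Average daily dose and percent dose intensity are also unaffected, provided their denominator is the duration including holds. This is a minor correction, worth making because the rule as written can produce an impossible value.

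**What to change.** In Appendix A, add for zero-dose records with no later dose:

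- Drop the end-of-treatment last dose as a milestone. The upper limit is the decision date, or the data cutoff if treatment is ongoing, without subtracting a day.
- A fully missing stop date is set to that limit.
- A partial stop date keeps its recorded month and year, is imputed by the existing rule, and is capped at that limit.
- An imputed stop may not precede the start of the same record.

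In SAP 6.5 and 6.6 B, state that a hold not followed by further dosing ends at the decision date (data cutoff if treatment is ongoing). Say in the Appendix A heading that the rule covers hold records.

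The cost is a few sentences and a small programming change. The decision date is already on the end-of-treatment CRF, so no new data are needed. SAP 4.8 already allows such a clarification as an addendum approved before unblinding.

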6.6 Study Treatment Modifications

Treatment modifications (holds and reductions) occurring due to AE will be summarized by treatment arm for subjects in the Safety population as follows:

A. Summaries for dose reductions due to AE

Categorical summaries for:

- Subjects with any dose reduction
- Cabozantinib dose levels (140 mg, 100 mg, 60 mg, 40 mg, 20 mg, 0mg) received by a subject, respective to treatment group
- Lowest cabozantinib dose level received (excluding dose holds)
- Last cabozantinib dose level received (excluding dose holds)
- Last cabozantinib dose level received (including dose holds)

Descriptive statistics for:

- Number of dose reductions
- Duration of treatment at each cabozantinib dose levels (140 mg, 100 mg, 60 mg, 40 mg, 20 mg, 0mg) received by a subject
- Time in days to first dose level reduction

- Time in days to second dose level reduction
- B. Summaries for dose holds due to AE:
 - Subjects with any dose hold, and dose hold ≥ 7 days, ≥ 14 days, and ≥ 21 days
 - Descriptive statistics for number of dose holds per subject, and classified into 1, 2, 3, and >3
 - Descriptive statistics for duration of dose holds per subject, calculated as (stop date of hold start date of hold + 1), and classified into ≥ 7 days, ≥ 14 days, and ≥ 21 days
 - Descriptive statistics for duration of total dose holds, calculated as (stop date of hold start date of hold + 1), and classified into \geq 7 days, \geq 14 days, and \geq 21 days
 - Descriptive statistics for time to first dose hold, time to first dose hold that was ≥ 7 days,
 ≥ 14 days, and ≥ 21 days. The time to dose hold is calculated as (start date of the hold first dose date + 1)
 - Descriptive statistics for time to second dose hold, time to second dose hold that was ≥ 7 days, ≥ 14 days, and ≥ 21 days
- C. Summaries for dose modifications (holds and reductions) due to AE:
 - Frequency counts and percentages for subjects with any dose modifications
 - Descriptive statistics for number of dose modifications per subject
 - Descriptive statistics for time in days to the first dose modification (see Appendix D)
 - Descriptive statistics for time in days to the second dose modification (see Appendix D)

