4.4 Missing and Partial Data

In general, other than for partial dates, missing data will not be imputed and will be treated as missing. The algorithms for imputation of partial dates vary depending upon the parameter. These are presented in Appendix A.

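### The time-to-first and time-to-second dose reduction, hold and modification summaries include only subjects who had the event, so read alone they can hide or shrink a tolerability difference between the arms

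*SAP*

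**What the plan says.** SAP 6.6 covers dose holds and reductions due to adverse events, which "will be summarized by treatment arm for subjects in the Safety population as follows". Its descriptive statistics include "Time in days to first dose level reduction", the time to the second reduction, and the times to first and second hold and modification. It names no censoring rule and no time-to-event method.

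Appendix D gives the algorithms:

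- **First modification:** "Time from first dose to earliest of A or C (among those", and the cell goes on to name subjects with either A (first reduction) or C (first hold).
- **Second modification:** also restricted, "among those with 2 or more of A, B or C".
- **First reduction:** only "Time from first dose to (A) above". The second reduction is worded in the same way from milestone B. Neither row states a restriction.
- **Holds:** there is no row. SAP 6.6 itself defines the time as hold start minus first dose plus one day.

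SAP 4.4 adds: "In general, other than for partial dates, missing data will not be imputed and will be treated as missing".

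SAP 6.6 also plans summaries that do not condition on the event, among them "Subjects with any dose reduction" and "Frequency counts and percentages for subjects with any dose modifications". SAP 6.5 adds exposure duration, average daily dose and percent dose intensity.

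**The concern.** Whether a subject ever needs a reduction, hold or modification is decided after randomization and may depend on dose. A median taken only among subjects who had the event compares two groups selected by outcome, and leaves out those who tolerated treatment without a change. If 60 mg spares some subjects any reduction but leaves the timing unchanged in the rest, the two medians agree although the arms differ.

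Tolerability is the reason for testing 60 mg: Protocol 1.5.1 expects a lower dose to bring fewer reductions and interruptions. The protocol synopsis also reports a median time to first reduction for the prior phase 3 trial, so a reader is likely to compare the same statistic between arms here.

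**Working it through.** The documents state no figure for these summaries, so there is none to reproduce. The check has two parts: which subjects enter, and how far the result can mislead.

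**Who enters.** For modifications Appendix D says so. For reductions, a subject who never reaches milestone A has no date A, hence no value. With no censoring and no imputation, that subject drops out. The same holds for hold times, because a subject with no hold has no hold start date.

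**Inputs.**

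- Share reduced at 140 mg in the prior trial: 80.8% (Protocol synopsis; rounded to 80% in model 1).
- Median time to first reduction there: 44.0 days (Protocol synopsis), read here as the median among those reduced, which is an assumption.
- Time on treatment: expected median 11 months (Protocol 3.2), 11 × 30.4375 ≈ 335 days; prior-trial median exposure 315 days (Protocol 1.4.3.2.1).
- Share reduced at 60 mg: not given. Assumed 52%, with a range of 30% to 70%.
- Assumed throughout: exponential times, and discontinuation independent of reduction.

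**Model 1: 60 mg changes who is reduced, not when.** Discontinuation hazard c = ln 2/335 = 0.00207 per day. Observed times among those reduced have total hazard λ + c = ln 2/44 = 0.01575, so λ = 0.01368. If a share s is observed to be reduced, the susceptible share is p = s(λ + c)/λ = s/0.8687.

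- Conditional median: ln 2/(λ + c) = 44 days for any s.
- Kaplan-Meier median, censoring at discontinuation: −ln(1 − 0.5/p)/λ.
- Cumulative incidence with discontinuation competing: s[1 − exp(−(λ + c)t)], at 91.3 days (3 months) and 183 days (6 months).

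| Share reduced | p | Conditional median | Kaplan-Meier median | 3 months | 6 months |
|---|---|---|---|---|---|
| 80% | 0.921 | 44 d | 57 d | 61% | 76% |
| 70% | 0.806 | 44 d | 71 d | 53% | 66% |
| 60% | 0.691 | 44 d | 94 d | 46% | 57% |
| 52% | 0.599 | 44 d | 132 d | 40% | 49% |
| 40% | 0.460 | 44 d | not reached | 31% | 38% |
| 30% | 0.345 | 44 d | not reached | 23% | 28% |

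A simulation with 94 subjects per arm, with 80.8% against 40% reduced, the same timing and no discontinuation, agrees. A rank test on the conditional times rejects in 5% of runs, its null rate. A test of the two percentages rejects in essentially all.

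**Model 2: constant hazard of reduction.** c = ln 2/315 = 0.00220, and h = c × 0.808/0.192 = 0.00926. The share reduced is h/(h + c), the conditional median ln 2/(h + c) and the Kaplan-Meier median ln 2/h.

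| Reduction hazard | Share reduced | Conditional median | Kaplan-Meier median |
|---|---|---|---|
| 140 mg | 80.8% | 60 d | 75 d |
| Halved | 67.8% | 101 d | 150 d |
| One quarter | 51.3% | 154 d | 299 d |

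Here the conditional median moves, but by less: a ratio of 101/60 ≈ 1.7 against 150/75 = 2.0 when halved, and 154/60 ≈ 2.5 against 299/75 ≈ 4.0 at one quarter. This model gives 60 days at 140 mg rather than 44, so it fits the prior trial's timing less well than model 1.

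**Whether the percentages are enough.** In model 2, halve both the reduction and the discontinuation hazard at 60 mg. The share ever reduced is then 80.8% in both arms. The 3-month cumulative incidence is 0.808 × [1 − exp(−0.01146 × 91.3)] = 52% at 140 mg and 0.808 × [1 − exp(−0.00573 × 91.3)] = 33% at 60 mg. The conditional medians do differ here, at 60 and 121 days.

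**The case against.** The strongest reply is that nothing important rests on these times. The listed endpoint is the frequency of dose modifications (SAP 2.2.3), and SAP 6.6 reports the shares with any reduction, hold or modification, by arm, in the whole Safety population. SAP 6.5 adds dose intensity, and SAP 8.1 adds adverse events leading to reduction, hold or discontinuation. With 94 per arm and 80.8% reduced at 140 mg, a comparison of percentages has power 0.88 against 60% (0.40 against 70%). SAP 8 calls any comparison of safety between the arms exploratory. All of this stands, and it sets the severity.

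A reader might infer that the tolerability comparison as a whole conditions on the outcome. The documents do not support that: only the time summaries do. Nor does Appendix D state the restriction for every time. It is written for the two modification rows and only implied for reductions and holds.

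The 44 against 44 result is also built in by assuming that 60 mg changes who is reduced but not when. Model 2 gives attenuation, not concealment.

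Finally, Kaplan-Meier with censoring at discontinuation is not a neutral benchmark. Protocol 3.5.3 lists unacceptable side effects as a reason to stop, so that censoring may be informative, and its medians describe a setting without discontinuation. This too stands, and it is why the fix treats discontinuation as a competing event.

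The reply does not remove the point. Crude percentages take no account of differing time on treatment. Exposure is tabulated separately, but no planned summary gives risk over time in all treated subjects.

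**Conclusion.** The point holds for the time-to-first and time-to-second reduction, hold and modification summaries only. They condition on a post-randomization outcome, explicitly for modifications and by implication for reductions and holds. Read alone, they can show no difference (44 against 44 days, with 80% and an assumed 52% reduced and unchanged timing) or an attenuated one (60 against 154 days, where Kaplan-Meier medians are 75 and 299). These sizes rest on assumed 60 mg reduction rates, exponential times and independent discontinuation.

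The unconditional percentages would show a difference in the share modified, though they can miss one when better tolerability also lengthens treatment. The item is minor and exploratory, and no primary or secondary efficacy conclusion depends on it. It is still worth correcting, because tolerability is the rationale for 60 mg and a better summary needs no new data.

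**What to change.** In SAP 6.6 and Appendix D, add for all Safety subjects, by arm, the cumulative incidence of first adverse-event-related reduction, first hold and first modification. Treat treatment discontinuation and death as competing events, censor at data cutoff, and report the 3- and 6-month rates. Show the incidence of discontinuation alongside, since a lower reduction rate can also arise from more early stopping. Kaplan-Meier estimates censored at discontinuation may be given as supportive.

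Keep the existing time summaries, but label each with its denominator (subjects with the event, out of all treated). State that restriction for the reduction rows in Appendix D and for holds, as is already done for modifications.

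The cost is a little extra programming. The dates are already needed for the planned summaries, and neither data collection nor sample size changes.
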